1. AMENDMENT HISTORY

Initial version 1.0 issued 22/Sep/2021

Amendment No.	Protocol Version No.	Date issued	Author(s) of changes	Details of Changes made

2. SYNOPSIS

Study Title	Safe and Effective Headgear Accessory for Exercise-Induced Laryngeal Obstruction Studies (HALOS) – a Device Development Study.
Internal ref. no.	SP0707
Type of study	Interventional
Trial Design	Single Group Assignment.
Trial Participants	Adults with suspected Exercise-Induced Laryngeal Obstruction (EILO) capable of undertaking a Continuous Laryngoscopy during Exercise (CLE) test.
Planned Sample Size	30 participants.
Follow-up duration	There will be no follow-up.
Planned Trial Period	12 months.
Primary Objective	Ensure the HALOS headgear is suitable for facilitating CLE tests.
Secondary Objectives	
 • Validate risk scores identified in risk management documentation. • Validate mitigations of hazards identified in risk management documentation. • Uncover previously unforeseen hazards, especially any related to usability.
Primary Endpoint	Device effectiveness , measured by the proportion of CLE tests where the endoscopy image was clear and stable enough to allow a diagnosis of EILO to be confirmed or ruled out.
Secondary Endpoints	
i) Device usability rating, measured by the fraction of subjective usability ratings ≥ 4 on the post-test questionnaire. Clinician-reported usability will be scored on a five-point LIKERT scale¹ ranging from 1 (very hard to use) to 5 (very easy to use). Observations will be made throughout the session.
 
ii) Device usability subjective feedback, focussing on any clinician-reported concerns regarding set-up, operation and cleaning.
 
iii) Device tolerability ratings, measured by the fraction of subjective tolerability ratings ≥ 3 on the post-test questionnaire. Participant-reported tolerability will be scored on a four-point LIKERT scale ranging from 1 (very intolerable) to 4 (very tolerable).
 
iv) Device tolerability subjective feedback, focussing on any participant-reported concerns regarding the comfort of the headgear including how hot their head felt, weight of the headgear, how secure the headgear felt and the impact of the headgear on their performance during the investigation.

Device Name	Headgear Accessory for Laryngeal Obstruction Studies (HALOS)

¹ The LIKERT scale is a widely used type of psychometric response scale in which responders specify their level of agreement to a statement typically in five points (Preedy & Watson, 2010). Empirical evidence shows this scale has 90% reliability and 89% validity (Louangrath, 2018).

Manufacturer Name	Medical Physics and Clinical Engineering, Liverpool University Hospitals NHS Foundation Trust
Principle intended use	The device is intended to be used with an endoscope and enable the larynx to be observed during CLE tests. It is intended for use on patients with suspected EILO.
Length of time use the device has been in use.	The device is not currently in use as this is a new design.

3. ABBREVIATIONS

AE	Adverse event
ADE	Adverse Device Effect
CI	Chief Investigator
CLE	Continuous Laryngoscopy during Exercise
CRF	Case Report Form
CRO	Contract Research Organisation
CT	Clinical Trials
CTA	Clinical Trials Authorisation
EILO	Exercise Induced Laryngeal Obstruction
GCP	Good Clinical Practice
GP	General Practitioner
HRA	Health Research Authority
ICF	Informed Consent Form
ICH	International Conference of Harmonisation
LUHFT	Liverpool University Hospitals NHS Foundation Trust
MHRA	Medicines and Healthcare products Regulatory Agency
NHS	National Health Service
NRES	National Research Ethics Service (previously known as COREC)
PI	Principal Investigator
PIL	Participant/ Patient Information Leaflet
R&I	R&I Department
REC	Research Ethics Committee
SAE	Serious Adverse Event
SADE	Serious Adverse Device Effect
SIL	Subject Information Leaflet (see PIL)

SOP	Standard Operating Procedure
TMF	Trial Master File
USADE	Unanticipated Serious Adverse Device Effect

4. BACKGROUND AND RATIONALE

4.1 Condition

Exercise-induced laryngeal obstruction (EILO) is a condition in which closure of the larynx occurs during high-intensity exercise. The reduction in airflow due to airway narrowing results in breathlessness and wheeze, and the patient may also report a cough or throat discomfort that can persist for some time (Hall, et al., 2016).

Whilst symptoms usually resolve soon after stopping exercise, an episode of EILO can impact on athletic performance and in competitive sports people can thereby impact on their careers. In all individuals, sudden onset EILO can lead to breathlessness inducing significant fear, panic, loss of control and pain (Carel, et al., 2015).

4.2 Current Practice

Due to the presentation of the condition, there is a large differential diagnosis, and the patient is often diagnosed with exercise-induced asthma (bronchoconstriction) and prescribed a short-acting bronchodilator. However, there are differences between the two conditions. The symptoms in EILO arise during high-intensity exercise and settle rapidly (within 5 minutes of exercise cessation), whereas with exercise-induced bronchoconstriction the symptoms onset following exercise cessation (5-10 minutes). Additionally, the wheeze of EILO is typically high pitched and occurs during the inspiratory phase of the breathing cycle. However, narrowing of the lower airway results in a polyphonic basal wheeze, and occurs during the expiratory phase (Hall, et al., 2016).

Incorrect diagnosis can lead to a large pharmacological burden for the patients with many being incorrectly treated with regular doses of steroids with little or no clinical effect (Newman, et al., 1995; Traister, et al., 2013).

EILO is often diagnosed in young athletes, and a cross-sectional study of 12-13 year-olds in Sweden found a prevalence of approximately 6% (Johansson, et al., 2015). However, a study found that EILO may be as prevalent as exercise-induced bronchoconstriction, and these two conditions may coexist in over 10% of individuals (Nielsen, et al., 2013).

Whilst clinical features can differentiate EILO from exercise-induced bronchoconstriction, studies have shown that discriminatory questions (e.g. difficulty breathing in when exercise) have a poor diagnostic value. A study has also shown that a diagnosis of EILO cannot be made by resting or post-exercise spirometry, or by peak flow measurement (Christensen, et al., 2013). Additionally, as EILO presents during high-intensity exercise, investigations during resting state may not provide a reliable diagnosis.

Clinicians have observed patients, either in person or by video recording, as they develop symptoms to review the presentation and onset. However, this method of investigation has not yet been formally studied (Hall, et al., 2016).

The gold standard for a diagnosis of EILO is a continuous laryngoscopy exercise (CLE) test, in which a flexible endoscope is used to monitor the laryngeal movement in real-time during exercise (Hall, et al., 2016). The tip of the endoscope is positioned in the mesopharynx (identified in Figure 1) by the clinician, who uses the live image from the endoscope to guide its position. A securing headgear is essential to keep the endoscope in a fixed position while the patient exercises, both to achieve a stable image and for the safety of the patient. An example of a CLE test set-up is displayed in Figure 2. This method of investigation is not currently offered by LUHFT, and other centres we have contacted provide the service using a non-CE/UKCA marked headgear.

[figure not shown]

Figure 1: showing the location of the mesopharynx, taken from (James F. Bosma M.D., 1986)

[figure not shown]

Figure 2: Continuous laryngoscopy exercise (CLE) test (Hall, et al., 2016)

4.3 Existing Research

Studies have been carried out to investigate EILO, and several mention the use of a specialised headgear (Hull, et al., 2019; Heimdal, et al., 2006; Olin, et al., 2016). However, there has been no formal research published regarding the headgear itself.

4.4 Rationale for Current Study

A headgear is necessary to carry out CLE tests for the investigations of EILO, as the endoscope must be kept stable for both image quality and patient safety. There is no commercial option existing on the market at present, and other centres have manufactured their headgear in-house (Liverpool Heart and Chest Hospital (LHCH), Royal Brompton Hospital).

Without a specialised headgear it is not possible to carry out CLE tests at LUHFT, and patients are sent for investigations at LHCH. This study is an essential step in improving the care that can be offered by LUHFT for sufferers of EILO. Evaluating the in-house design of headgear is necessary to support its safe and effective clinical use in accordance with the Medical Device Directive (MDD) 93/42 and in the spirit of the European Medical Device Regulations (MDR) 2017/745. By producing an in-house manufactured headgear, it will enable LUHFT to provide an additional service for patients, avoiding the inconvenience to them of having to travel further afield.

Therefore, the hypothesis for this study is that the HALOS headgear is sufficiently effective for clinical use, and that the risks are understood adequately for an accurate benefit/risk ratio evaluation.

4.5 Regulatory Compliance

The device is intended to be used with an endoscope and enable the larynx to be observed during CLE tests. According to the MDD it is classified as an accessory for a medical device and therefore the MDD would apply. However, the headgear is not intended to be made commercially available or UKCA/CE marked, nor will it be used outside the Trust where it is manufactured. Consequently, as it is not being 'put into service' nor 'placed on the market', it is not subject to the requirements of the MDD. Nonetheless, the headgear has been specified, designed and manufactured following a Quality Management System (QMS) aligned with BS EN ISO 13485:2016 QMS requirements for medical devices, the MDD and European MDR. This includes Post Market Surveillance activities.

5. OBJECTIVES

5.1 Primary Objective

Ensure the HALOS headgear is suitable for facilitating CLE tests.

5.2 Secondary Objectives

Validate risk scores identified in risk management documentation.

Validate mitigations of hazards identified in risk management documentation.

Uncover previously unforeseen hazards, especially any related to usability.

6. TRIAL DESIGN

6.1 Summary of Trial Design

The study is an interventional clinical trial involving a single group of 30 participants undergoing a CLE test with the HALOS headgear.

Participants will be required to attend a single consultation and screening appointment to discuss the investigation procedure, and this will occur at least a week before the CLE test. Participants will then attend one appointment for the CLE test. There will be no follow up assessments using the headgear.

6.2 Primary and Secondary Endpoints/Outcome Measures

6.2.1 Primary Outcome Measure

Device effectiveness, measured by the proportion of CLE tests where the endoscopy image was clear and stable enough to allow a diagnosis of EILO to be confirmed or ruled out.

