6.2.2 Secondary Outcome Measures

- i) **Device usability rating**, measured by the fraction of subjective usability ratings ≥ 4 on the post-test questionnaire. Clinician-reported usability will be scored on a five-point LIKERT scale² ranging from 1 (very hard to use) to 5 (very easy to use). Observations will be made throughout the session.
- ii) **Device usability subjective feedback**, focussing on any clinician-reported concerns regarding set-up, operation and cleaning.
- iii) **Device tolerability ratings**, measured by the fraction of subjective tolerability ratings ≥ 3 on the post-test questionnaire. Participant-reported tolerability will be scored on a four-point LIKERT scale ranging from 1 (very intolerable) to 4 (very tolerable).
- iv) **Device tolerability subjective feedback**, focussing on any participant-reported concerns regarding the comfort of the headgear including how hot their head felt, weight of the headgear, how secure the headgear felt and the impact of the headgear on their performance during the investigation.

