6.4.4 Subsequent assessments

Following the consultation appointment, the participant will attend one investigation appointment to undergo the CLE test on-site at the Outpatient Department, Alexandra Wing, Broadgreen Hospital. There will be no follow-up assessments.

On the day of the investigation appointment, the Principal Investigator will address any questions or concerns before the investigation begins. If the participant still wishes to partake in the study, signed consent will be obtained from the participant. The right of the participant to refuse to participate without giving reasons will be respected. After the participant has entered the study the clinician remains free to give alternative treatment to that specified in the protocol at any stage if he/she feels it is in the participant's best interest, but the reasons

for doing so should be recorded. In these cases, the participants remain within the study for the purposes of data analysis.

Eligibility will be reviewed for any changes, ensuring that the participant meets the inclusion criteria and none of the exclusion criteria apply. As part of this, the circumference of the participant's head around the forehead will be measured and recorded. Signed consent will then be obtained. The participant will then undergo the CLE test following standard clinical practice.

The order of events of the aspects of the investigation related to the headgear will be:

1. The headgear is prepared for use.
2. The headgear is fitted onto the participant's head.
3. The endoscope is inserted into the participant.
4. The endoscope is fitted onto the headgear.
5. The CLE test is carried out.
6. The endoscope is removed from the headgear.
7. The endoscope is removed from the participant.
8. The headgear is removed from the participant.
9. The headgear is cleaned and stored.

Following completion of the CLE test, the participant will complete a questionnaire:

- How tolerable was the headgear during the investigation?
 - 1) Highly intolerable
 - 2) Intolerable
 - 3) Tolerable
 - 4) Highly tolerable
- Please tell us any concerns about the headgear, thinking about how comfortable it was, how hot your head felt, the weight of the headgear, how secure it felt and the impact of the headgear on your performance during the investigation.

Following the appointment, the clinician will complete a questionnaire including:

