- Was the endoscopy image clear and stable enough to allow a diagnosis of EILO to be confirmed or ruled out? (Note that participants are withdrawn from the study if the

CLE test is unable to allow a diagnosis of EILO to be confirmed or ruled out due to reasons unrelated to the headgear.)

- How easy was it to use the headgear?

- 1) Very hard to use;
- 2) Hard to use;
- 3) Neither hard nor easy to use;
- 4) Easy to use;
- 5) Very easy to use.

- Please record any concerns about the headgear, thinking particularly about set-up, operation and cleaning.

Data will be handled as detailed in Section 13 Data Handling and Record Keeping.

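### The primary endpoint is worded on image quality, and the plan does not say how to score a test left non-diagnostic because the headgear limited or stopped the exercise

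*Combined protocol and SAP*

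**What the plan says.** **Objective and endpoint.** Section 5.1 sets the aim: "Ensure the HALOS headgear is suitable for facilitating CLE tests". Section 6.2.1 takes device effectiveness as the primary outcome, "measured by the proportion of CLE tests where the endoscopy image was clear and stable enough to allow a diagnosis of EILO" to be made or excluded.

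**Data item.** The only item that scores the endpoint is the clinician question in Section 6.4.4: "Was the endoscopy image clear and stable enough to allow a diagnosis of EILO to be confirmed or ruled out". A note to that question says that participants are withdrawn when the "CLE test is unable to allow a diagnosis of EILO to be confirmed or ruled out due to reasons unrelated to the headgear".

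**Withdrawal.** Section 6.5 repeats that rule. It also lets the investigator withdraw a participant for any reason. Its examples include an adverse event or device effect that ends the test, and a headgear that cannot be worn. Withdrawn participants are replaced. Section 9.7 puts all eligible participants in the analysis but does not mention those withdrawn.

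**Exercise.** Section 4.2 notes that "as EILO presents during high-intensity exercise, investigations during resting state may not provide a reliable diagnosis". Section 7.1 gives the headgear's weight as 1.5 kg. Secondary outcome iv in Section 6.2.2 covers heat, weight, security and "the impact of the headgear on their performance during the investigation", collected as participant free text. Section 9.1 uses this feedback to reduce residual risks, not to judge effectiveness.

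**Test.** Section 9.1 compares the primary proportion with 49 in 50, derived from a tolerable rate of inadequate images of 1 in 50. Section 9.2 sets 30 participants for practical reasons, and Section 9.3 sets the level at 0.01.

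**Tolerability form.** Section 6.4.4: "Following completion of the CLE test, the participant will complete a questionnaire".

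**The concern.** The headgear can fail a CLE test in at least two ways. It can give a poor image, or it can stop the participant from exercising hard enough for the larynx to be judged under load. The endpoint, the question that scores it and the threshold are all worded on the first way. The plan foresees the second, since it asks participants about weight, heat and performance, but gives no rule for scoring it.

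The plan does not define adequate exercise, and it does not record whether a diagnosis was reached. A clear picture of a larynx that was never sufficiently stressed does not exclude EILO, on the protocol's own account of the condition. If such a test is scored as a success, or leaves the study and is replaced, the reported proportion overstates how often the headgear supported a usable test. That proportion feeds the internal clinical evaluation described in Section 16.

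**Working it through.** **Step 1. The three readings of one event.** Take a test with a clear, stable image that could not settle the diagnosis because the headgear limited or stopped the exercise.

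| Reading | Basis | Score |
|---|---|---|
| Literal | 6.2.1 and the 6.4.4 question ask about the image, and the image was adequate | Success |
| With the note | The 6.4.4 note removes non-diagnostic tests unrelated to the headgear, which implies that the remaining ones are answered no | Failure |
| Withdrawal | 6.5: device effect ending the test, headgear cannot be worn, or any other reason the investigator finds necessary | Leaves the study and is replaced |

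The first and third readings keep a headgear failure out of the failure count. Only the second records it.

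**Step 2. The plan's own figures.** The reference proportion agrees with its basis: 1 − 1/50 = 49/50 = 0.98. No formula lies behind n = 30, so there is no sample size to reproduce.

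**Step 3. What rescoring does at n = 30.** Each test moved from success to failure lowers the estimate by 1/30 = 3.3 points. The exact lower-tail p-value is P(X ≤ s) for X ~ Binomial(30, 0.98).

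| Successes s | Proportion | P(X ≤ s) |
|---|---|---|
| 29 | 96.7% | 0.455 |
| 28 | 93.3% | 0.121 |
| 27 | 90.0% | 0.022 |
| 26 | 86.7% | 0.0029 |

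The plan does not state sidedness. For these four rows the two-sided exact p-values are the same. At the 0.01 level a shortfall is flagged only from four failures. In the other direction, 30/30 gives P(X ≥ 30) = 0.98^30 = 0.545, so the formal test cannot show performance above 98% under any scoring.

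**Step 4. Illustration with assumed rates.** The documents give no rate of headgear-limited tests. Assume that the image is adequate in 98% of tests, and that a share q of those is left non-diagnostic by the headgear. The rate of useful tests is then 0.98 × (1 − q), and the expected number affected is 30 × 0.98 × q.

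| q (assumed) | Useful-test rate | Expected affected tests | P(X ≤ 26) if failures | P(X ≤ 26) if successes |
|---|---|---|---|---|
| 2% | 96.0% | 0.59 | 3.0% | 0.3% |
| 5% | 93.1% | 1.47 | 14.9% | 0.3% |
| 10% | 88.2% | 2.94 | 47.9% | 0.3% |

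Under the literal reading, the chance of flagging a shortfall does not respond to q at all.

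**The case against.** The strongest reply is that the endpoint is not image clarity alone. The image must be good enough to permit a diagnosis. The note beside the question also makes most sense if headgear-related non-diagnostic tests are answered no. This stands. A reader might infer that the plan scores such tests as successes, but no passage says so; that is one available reading.

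A reader might also infer that these tests must stay in the analysis because their cause is the headgear. Section 6.5 does not support that either, since it offers withdrawal routes that can be headgear-related. For some stopped tests the risk is exclusion and replacement, not misclassification.

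Three further points have weight:

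- **Effect on the formal result.** Three rescored tests (27/30, p = 0.022) would not reach 0.01. That one failure takes the estimate below 98% is a consequence of n = 30, whatever the failure's cause. What changes most readily is the reported proportion.
- **Tolerability.** One might infer that people who stop early never rate the headgear. Section 6.4.4 fixes only the timing of the form. It neither withholds the form from them nor ensures that they receive it, so a bias in tolerability is possible but not established.
- **Threshold.** The 49-in-50 figure was derived for image failures. Widening the endpoint without revisiting it would make the comparison inconsistent.

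It can also be said that placing the effect on performance under a secondary outcome was a choice. That is legitimate as far as it goes, but free text used for risk reduction does not settle how the primary endpoint is scored.

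**Conclusion.** The concern holds as a gap in the endpoint definition. One event can be a success, a failure or a replaced withdrawal, and the documents do not choose. Two of the three outcomes favour the device, so reported effectiveness can be biased upward relative to the objective in Section 5.1. The documents do not support saying that it is biased, or that the plan prescribes scoring such tests as successes.

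The size is 3.3 points per affected test. One such test in 30 takes 30/30 to 96.7%, below the reference but far from significant. The formal conclusion at 0.01 changes only when total failures reach four. How many tests are affected depends on a rate that the documents do not give; the 2% to 10% range above is an assumption. The point should be settled before data collection, because the cause of a non-diagnostic test is hard to reconstruct afterwards.

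**What to change.** - **CRF.** Add two closed items to the clinician questionnaire: (a) result: EILO confirmed, EILO excluded, or non-diagnostic; (b) if non-diagnostic, cause: image, other headgear cause, or unrelated to the headgear.
- **Sections 6.2.1, 6.4.4 and 6.5.** State that, for the analysis, every test left non-diagnostic for a headgear-related cause counts as a failure. This includes headgear-related withdrawals, which stay in the denominator and are not replaced there. Editing 6.2.1 and 6.4.4 alone would leave the withdrawal route open.
- **Section 9.1.** Confirm that the 49-in-50 reference applies to this definition. Report image-only adequacy against 49 in 50 as a supportive result.
- **Tolerability.** Give the form to everyone fitted with the headgear, whether or not the test was completed.

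The cost is two tick-box items and a few sentences, with no new procedure or reader. There are two downsides. The reported success proportion can only stay the same or fall. Attributing cause is a clinician's judgement, and in a single-group study it may be hard to separate the headgear's effect from the participant's own breathlessness. The plan already requires that judgement when it withdraws tests for reasons unrelated to the headgear.
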